#### 5.2.3. Overall Assessment of Scaling

Overall Assessment of Erythema will be performed according to the Schedule of Visits and Assessments ([Section 1.3](#)).

Overall Assessment of Scaling are static qualitative evaluations, involving an ordinal scale with 4 severity grades (reported only in integers of 0 to 3). Each grade is defined by a distinct and clinically relevant morphologic description that minimizes inter-observer variability.

**Every effort must be made for the same Evaluator to complete the Overall Assessment of Scaling for the subject at every study visit, particularly for Baseline and Week 8.**

## Overall Assessment of Scaling

[figure not shown]
Symptom	Score	Description
Scaling	0	None: No scaling evident on lesions
	1	Mild: Barely detectable, scattered, small flaking scales
	2	Moderate: Scales clearly visible and prominent
	3	Severe: Coarse, thick scales, with flaking into clothes or skin

### 5.2.4. Worst Itch-Numerical Rating Scale (WI-NRS)

Given that itch is an important symptom of seborrheic dermatitis, a WI-NRS assessment is included in the present study. A responder analysis will be performed to evaluate achievement of a 4-point reduction of WI-NRS, which has been described as optimal for demonstrating a level of clinically meaningful improvement in itch severity in other skin conditions, including other forms of eczema ([Yosipovitch 2019](#)) and psoriasis ([Kimball 2016](#)).

WI-NRS Assessment will be performed by subjects **daily** at home according to the Schedule of Visits and Assessments ([Section 1.3](#)) starting 7 days prior to the scheduled Baseline/Day 0 visit up to the Week 8/Day 56 visit. Subjects will be provided with a diary to record their daily WI-NRS assessments.

The WI-NRS has been developed as a simple, single item to assess the patient-reported severity of this symptom at its highest intensity during the previous 24-hour period. ([Naegeli 2015](#)). The WI-NRS will be determined by asking the subject's assessment of worst itch over the past 24 hours. The scale is from '0 to 10' ("no itch" to "worst imaginable itch").

### 5.2.5. Scalpdex

The Scalpdex ([Appendix 7](#)) will be performed by subjects according to the Schedule of Visits and Assessments ([Section 1.3](#)).

### 5.2.6. Dermatology Life Quality Index (DLQI) and Children's Dermatology Life Quality Index (CDLQI)

The DLQI (ages 17+ years) and CDLQI (ages 9-16 years, inclusive) will be performed according to the Schedule of Visits and Assessments ([Section 1.3](#)). The DLQI/CDLQI is a simple, self-administered and user-friendly validated questionnaire. The DLQI/CDLQI is designed to measure the health-related quality of life of patients suffering from a skin disease. The DLQI/CDLQI consists of 10 questions concerning patients' perception of the impact of skin diseases on different aspects of their health-related quality of life over the last week.

The DLQI ([Appendix 8](#)) will be completed by subjects ages 17 years and older. The CDLQI ([Appendix 9](#)) will be completed by caregivers of subjects ages 9-16 years.

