***Footnotes from table above:***

- a Subjects that terminate early should return to the study site for the Week 8 assessments.
- b Limited physical examination: skin (including assessment of Fitzpatrick Skin Type at Screening only), lungs, and heart only.
- c To be collected at Screening, Baseline/Day 0, Week 4/Day 28, and Week 8/Day 56. For subjects <18 years of age, if the Baseline/Day 0 visit occurs within 3 weeks of Screening, the Screening lab results may be utilized.
- d Height will be collected at Baseline and Week 8. Weight will be collected at all study visits. Subject to void prior to weight.
- e IGA will be a 5-point scale ranging from clear (0) to severe (4). **IGA should be completed prior to other physician assessments and by the same Evaluator at each study visit.** Overall Assessment of Erythema (0-3 scale) and Overall Assessment of Scaling (0-3 scale) will be completed.
- f Total BSA affected by seborrheic dermatitis will be determined by the subject's hand method, where the subject's hand (including fingers) surface area is assumed to equal 1% of body surface area.
- g The DLQI will be completed by subjects  $\geq$ 17 years of age. The CDLQI will be completed for subjects 9 to 16 years old, inclusive.
- h WI-NRS will be completed by subjects daily at home starting 7 days prior to the Baseline/Day 0 visit to Day 56 (Week 8) visit. Daily WI-NRS will be completed in the evening prior to IP application (except at Baseline and Week 2 when IP is applied at the clinic).
- i Local tolerability assessments to be recorded prior to IP application for the Investigator assessment of skin irritation (Berger and Bowman skin irritation score) and 10-15 minutes post IP application for the subject's '0-3' burning/stinging assessment. **Note for investigator tolerability assessments: reactions at the site of IP application, which may occur post-Baseline, should be differentiated from the preexisting inflammation associated with the subject's seborrheic dermatitis. At Week 4 and Week 8, subjects will provide a recall assessment of burning/stinging experienced post IP application on the day prior to the clinic visit.**
- j An assessment for hypopigmentation and hyperpigmentation will be performed by the Investigator at all visits.

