## APPENDIX 9. CHILDREN'S DERMATOLOGY LIFE QUALITY INDEX (CDLQI)

Subject Number:  
Age:

Diagnosis:  
Date:

CDLQI  
SCORE:

**The aim of this questionnaire is to measure how much your skin problem has affected you OVER THE LAST WEEK. Please tick ✓ one box for each question.**

1. Over the last week, how itchy , " scratchy ", sore or painful has your skin been?	Very much 		
	Quite a lot 		
	Only a little 		
	Not at all 		
2. Over the last week, how embarrassed or self conscious , upset or sad have you been because of your skin?	Very much 		
	Quite a lot 		
	Only a little 		
	Not at all 		
3. Over the last week, how much has your skin affected your friendships ?	Very much 		
	Quite a lot 		
	Only a little 		
	Not at all 		
4. Over the last week, how much have you changed or worn different or special clothes/shoes because of your skin?	Very much 		
	Quite a lot 		
	Only a little 		
	Not at all 		
5. Over the last week, how much has your skin trouble affected going out , playing , or doing hobbies ?	Very much 		
	Quite a lot 		
	Only a little 		
	Not at all 		
6. Over the last week, how much have you avoided swimming or other sports because of your skin trouble?	Very much 		
	Quite a lot 		
	Only a little 		
	Not at all 		
7. Last week , was it school time?		If school time: Over the last week, how much did your skin problem affect your school work ?	Prevented school 
			Very much 
			Quite a lot 
			Only a little 
			Not at all 
OR			
was it holiday time?		If holiday time: How much over the last week, has your skin problem interfered with your enjoyment of the holiday ?	Very much 

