### REMOTE DATA COLLECTION

In the event subjects are unable to complete protocol-specific assessments onsite, study sites may collect data from subjects remotely via telephone and/or by traditional mail or email. The method used for data collection must be clearly documented in the source. Whenever possible, sites should adhere to the protocol visit window for remote data collection. Screening and Baseline (Day 0) visits/assessments must be performed in the clinic and must NOT be completed remotely. If necessary, these visits can be delayed ensuring they are conducted in the clinic and not remotely.

Data collection by phone may be performed. Subjects are contacted via telephone and site staff will collect data verbally for all critical data points applicable. Subject responses should be recorded in the site source documents. Data collected remotely should be entered into the EDC system (iMedidata Rave).

Data collection by mail or email may also be performed for applicable assessments. Site staff will contact subjects via traditional mail or email to collect data using paper versions of study questionnaires. C-SSRS cannot be collected by mail/email as this requires subject interview by site staff.

Investigator assessments and subject questionnaires normally completed during on-site visits should be completed on the appropriate paper source documents and entered in the EDC. The following subject assessments/questionnaires are approved to be collected via telemedicine/remote:

- C-SSRS
- PHQ-8/PHQ-A/CDI-2
- DLQI/CDLQI
- Scalpdex
- Subject Local Tolerability
- Adverse Events
- Concomitant medication

The following Investigator assessments cannot be completed via telemedicine/remote:

- IGA
- BSA
- Investigator Local Tolerability
- Pigmentation Assessment
- Overall Assessment of Erythema
- Overall Assessment of Scaling
- Subject Weight

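### Protocol 5.2.6 presents the CDLQI as the patient's own report but assigns it to caregivers, and nothing fixes or records who answers

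*Protocol*

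**What the plan says.** Protocol 5.2.6 makes two statements that do not fit together. The general description reads "The DLQI/CDLQI is a simple, self-administered and user-friendly validated questionnaire" and adds that it "consists of 10 questions concerning patients' perception of the impact of skin diseases". The last sentence of the section, the only one in either document that names a CDLQI respondent, says the form "will be completed by caregivers of subjects ages 9-16 years".

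The form printed in Appendix 9 speaks to the child: "The aim of this questionnaire is to measure how much your skin problem has affected you". Footnote g to the schedule in Protocol 1.3 says "The CDLQI will be completed for subjects 9 to 16 years old, inclusive", and footnote g to SAP Table 1 has the same wording. In both footnotes the DLQI is completed by the subject, whereas the CDLQI is completed on the subject's behalf or for the subject's record. The reader is not told which.

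SAP 6.1.7 scores the CDLQI from its ten items and has a rule for missing items. It has no variable for the respondent. SAP 8.3 analyzes change and percent change at Weeks 2, 4 and 8 on observed data, by ANCOVA with treatment, pooled site, baseline IGA and the baseline score.

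**The concern.** Two things are at stake.

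The first is what the score means. A caregiver who follows 5.2.6 to the letter answers questions addressed to someone else, including how embarrassed or upset that person has felt. The result is a proxy rating, but the protocol describes the instrument as the patient's perception, and the table titles in SAP 14.1 do not say otherwise. A reader of the study report could not tell whose view is shown.

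The second is comparability over time. The endpoint is a within-subject change. A site that goes by the form may hand it to the child, and a site that goes by the last sentence of 5.2.6 may hand it to the parent. Nothing stops this from differing between visits of one subject. Appendix 11 adds a possible route: Baseline must take place in the clinic, but later CDLQI forms may be collected by telephone, mail or email. If the respondent changes, part of the recorded change may come from who answered, and the planned analysis could not show it.

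**Working it through.** The documents give no figure to reproduce, so the check compares the text and then works through the consequence.

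**1. Places that bear on the respondent**

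| Place | What it implies |
|---|---|
| Protocol 5.2.6, description | The patient, without an interviewer; the patient's perception |
| Protocol 5.2.6, last sentence | The caregiver, ages 9 to 16 |
| Protocol 1.3 and SAP Table 1, footnote g | Not stated |
| Protocol Appendix 9, form | Worded to the child |
| Protocol Appendix 11, remote collection | CDLQI listed under "The following subject assessments/questionnaires are approved to be collected via telemedicine/remote"; no respondent named |
| SAP 6.1.7 and 8.3 | No respondent variable or same-respondent rule |

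The Appendix 11 list does not settle the matter, because it also contains the CDI-2, which is a parent report.

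**2. How the protocol treats comparable instruments**

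Where a proxy is clearly intended, the protocol says so and supplies a proxy form. The CDI-2 for ages 9 to 11 is called a parent report in footnote k and 5.1.9, and its items in Appendix 4 are statements a parent makes about the child. No proxy-worded CDLQI is supplied. The daily WI-NRS (5.2.4) and the Scalpdex (5.2.5) are given to subjects with no age exception, so the same children report their own itch and scalp impact. No reason is given for treating the CDLQI differently.

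**3. Consequence under each pattern of response**

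- Caregiver at every visit: the change contains no respondent switch, but the score is a proxy score.
- Child at every visit: no switch, and the score is what 5.2.6 describes, although its last sentence has not been followed.
- Respondent differs between Baseline and a later visit: the change contains the difference between the two respondents.

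**4. Effect of switching on the arm comparison**

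Let *q* be the share of children in an arm whose respondent changes between Baseline and the visit, and *s* the average shift in score that such a change causes.

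- Shift in the arm's mean change = *q* × *s*
- Shift in active minus vehicle = *s* × (*q*_active − *q*_vehicle)
- Added variance per subject, with *s* taken as fixed = *s*² × *q* × (1 − *q*)

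The documents give neither *q* nor *s*. Purely to show how the formulas behave, assume *s* = 1 to 3 points on the 0 to 30 scale and *q* = 10% to 30%:

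- Equal switching in both arms: each arm's mean shifts by 0.1 × 1 = 0.1 to 0.3 × 3 = 0.9. The between-arm shift is *s* × 0 = 0.0. Added variance runs from 1 × 0.1 × 0.9 = 0.09 to 9 × 0.3 × 0.7 = 1.89.
- Unequal switching, 30% versus 10%: the between-arm shift is 0.2 × 1 = 0.2 to 0.2 × 3 = 0.6.

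These inputs are assumptions and not estimates, and the point does not depend on them. What matters is the structure: the treatment comparison is displaced only if switching differs by arm.

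**The case against.** The strongest reply is that there is an instruction and it is clear: only one sentence names a respondent, and it names the caregiver. On this view self-administered means only that no interviewer is used, and footnote g is compatible with caregiver completion because it changes preposition between the DLQI and the CDLQI. That largely stands against any suggestion that a site has three equally valid instructions to choose from. It does not remove the conflict with the patient-perception description or with a form that addresses the child.

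A reader might go further and infer that the change from Baseline is confounded with the respondent, or that the treatment effect is biased. The documents do not support either. Nothing in them shows that respondents switched. A steady difference between sites does not by itself distort within-subject change, randomization is stratified by site, and pooled site is in the model. The trial is double-blind, and no passage links a change of respondent to treatment. Nor can a size in points be claimed, because the documents give neither the number aged 9 to 16 nor the gap between child and caregiver scores.

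It is also fair to say that keeping the caregiver and labelling the score as proxy-reported would remove the contradiction. Whether the instrument is valid when completed by a proxy cannot be judged from these documents. The child is the better choice here because the protocol's own description and form already presuppose it.

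**Conclusion.** The inconsistency is real and neither document resolves it. As written, the CDLQI tables would present a caregiver's rating as the child's own view. If respondents change between visits, the within-subject change can also reflect who answered, and the planned data would not reveal it.

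Severity is minor. Only subjects aged 9 to 16 are affected, and only an other secondary endpoint, which SAP 8.1 places outside the testing strategy. The primary endpoint and the alpha-controlled secondary endpoints are untouched. For active versus vehicle the expected consequence is added noise and unclear meaning, not bias. That rests on the assumption that any switching is unrelated to arm, which blinding and randomization make reasonable. In what is likely to be a small subgroup, a chance imbalance in switching could still occur.

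**What to change.** **Text.** In Protocol 5.2.6, replace the caregiver sentence with a statement that the child completes the CDLQI, with help in reading only, and that the respondent is the same at every visit. Align footnote g in Protocol 1.3 and in SAP Table 1. Add a field to the form that records the respondent at each visit. The cost is one sentence, two footnotes, a site instruction and one data field.

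**Data already collected.** SAP Section 1 dates database lock to 17-May-2022 and unblinding to 19-May-2022, so a text change cannot repair this trial's data. The sponsor should check whether source records show who completed each CDLQI and, if so, report the respondent by visit and arm. An analysis limited to pairs with the same respondent is acceptable as a labelled sensitivity analysis only. As the main rule it would be an exclusion chosen after unblinding on a post-randomization variable, in a subgroup that may already be small. Where source does not show the respondent, the study report and Tables 14.2.6.3 and 14.2.6.4 should label the result as respondent unknown, or as proxy-reported if caregivers are known to have answered. The cost is a source query and a footnote.

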### **5.2.7. Body Surface Area (BSA)**

BSA assessments will be performed according to the Schedule of Visits and Assessments ([Section 1.3](#)).

The BSA affected by seborrheic dermatitis will be determined by the subject's hand method, where the subject's hand (including fingers) surface area is assumed to equal 1% of body surface area.

## **5.3. Other Evaluations**

### **5.3.1. Pharmacokinetics Assessment**

Pharmacokinetic (PK) samples will be collected according to the Schedule of Visits and Assessments ([Section 1.3](#)) for all subjects.

- PK will be evaluated through trough sampling at Week 4 and Week 8.

PK samples will be collected while the subject is having serum chemistries drawn, when applicable. Ensure the IP is not applied in the area where PK will be drawn.

### **5.3.2. Dermal Imaging**

Medical photography as supportive evidence of clinical outcome will be conducted by all sites using Canfield equipment. Photos will be obtained according to the Schedule of Visits and Assessments ([Section 1.3](#)). Photography should be focused on single lesions or specific body sections (e.g., arm). Body or half body photos should only be taken if necessary. For subjects with seborrheic dermatitis lesions on the face, scalp, and/or body, effort should be made to prioritize obtaining a photograph of the facial lesion(s). All efforts will be made to de-identify the subjects. Subjects who are unwilling to participate in the medical photography will be allowed to opt out of this procedure and documented on the informed consent. Refer to the current Photography Manual for instructions regarding photography.

## **5.4. Final Study Visit**

The approximate final study visit will occur at Week 8 (Day 56). The procedures performed during this visit are described in the Schedule of Visits and Assessments ([Section 1.3](#)). A 5-day scheduling window is allowed for this visit. Adverse events will be recorded as reported by the participant or and followed to resolution (as necessary) as outlined in [Section 5.7](#).

## **5.5. Early Termination Visit**

If a subject is withdrawn from the study, an early termination visit will be scheduled. This visit should include the procedures and assessments that would be performed at the Week 8 visit (Day 56). Subjects who withdraw consent from study participation, will not be required to perform an early termination visit.

## **5.6. Unscheduled Visit**

Unscheduled visits may be necessary to repeat testing following abnormal laboratory results, for follow-up of AEs, or for any other reason, as warranted in the judgement of the Investigator.

The following information will be collected for all subjects:

- Concomitant medications/procedures
- AEs

## **5.7. Adverse Events**

### **5.7.1. Adverse Event Definition**

An AE is defined as any untoward medical occurrence associated with the use of a drug in humans, whether or not considered drug related. An AE can therefore be any unfavorable and unintended sign (including an abnormal laboratory finding), symptom, or disease temporally associated with the use of an investigational product, whether or not related to the investigational product.

The definition of AEs includes worsening of a pre-existing medical condition. Worsening indicates that the pre-existing medical condition has increased in severity, frequency, and/or duration or has an association with a worse outcome. When recording such events, provide descriptions that the pre-existing condition has changed (e.g., worsening hypertension for a subject with pre-existing hypertension). A pre-existing condition that has not worsened during the study or involves an intervention, such as elective cosmetic surgery or a medical procedure while on study, is not considered an AE.

Progression of treatment indication including new or worsening of anticipated clinical signs or symptoms, which are collected as clinical efficacy variables and assessed as unequivocally associated with the disease progression and /or lack of efficacy, should NOT be reported as adverse events unless the disease progression is greater than anticipated in the natural course of the disease.

In general, abnormal laboratory findings without clinical significance (based on the investigator's judgment) are not to be recorded as AEs. However, abnormal laboratory findings that result in new or worsening clinical sequelae, or that require therapy or adjustment in current therapy, are considered AEs. Where applicable, clinical sequelae (not the laboratory abnormality) are to be recorded as the AE.

### **5.7.2. Serious Adverse Event**

The definitions and reporting requirements of the Food and Drug Administration (FDA)/ICH Guidelines for Clinical Safety Data Management, Definitions and Standards for Expedited Reporting, Topic E2A will be adhered to. Mandatory reporting of all serious unexpected adverse drug reactions (SUSARs) to Health Canada [as per C.05.014 (1) of the FDR] will be adhered. If any AEs are serious, as defined by ICH Guidelines for Clinical Safety, required procedures will be followed.

As SAE is defined as any AE that, in the view of either the PI or Sponsor, meets at least 1 of the following serious criteria:

- Fatal
- Life-threatening (places the subject at immediate risk of death)
- Requires inpatient hospitalization or prolongation of existing hospitalization
- Results in a persistent or significant incapacity/disability
- Congenital anomaly/birth defect
- Other important medical events that, based upon appropriate medical judgment, may jeopardize the subject and may require medical or surgical intervention to prevent one of the outcomes listed in the above definition

Hospitalization does not include the following:

- Rehabilitation facilities, hospice facilities or respite care (e.g., caregiver relief)
- Nursing homes or skilled nursing facilities
- Emergency department visits
- Same day surgeries (as outpatient/same day/ambulatory procedures)
- <24 hour admissions for observation or evaluation

Hospitalization or prolongation of hospitalization in the absence of a precipitating, clinical AE is not in itself an SAE. Examples include:

- Admission for treatment of a preexisting condition that did not worsen
- Hospitalizations for cosmetic elective surgery, social, and/or convenience admissions
- Pre-planned treatments or surgical procedures should be noted in the baseline documentation for the individual subject
- Diagnostic and therapeutic procedures, such as surgery, should not be reported as AEs; however, the medical condition for which the procedure was performed should be reported if it occurs during the reporting period and meets the definition of an AE. For example, an acute appendicitis that begins during the AE reporting period should be reported as an AE, and the resulting appendectomy should be recorded as treatment of the AE.

Unexpected is defined as an AE that is not listed in the IB or is not listed at the specificity or severity that has been observed; or is not consistent with the risk information described in the general investigational plan or study documentation.

